1.2. Study Design

This is a Phase 2, proof-of-concept, placebo-controlled, double-blind, randomized study in adult participants with moderately to severely active RA who have had an inadequate response to csDMARDs, or to bDMARDs/tsDMARDs. Participants will be administered LY3462817 or placebo IV Q4W.

Screening Period (Visit 1, Days -42 to -1)

Participants will sign the informed consent document(s) at Visit 1, prior to completion of any procedures. Participants will be evaluated for study eligibility ≤ 42 days prior to the baseline visit (Visit 2).

Period 1: Double-blind Treatment (Visits 2 to 6; 12 weeks)

At the baseline visit (Visit 2), participants who fulfill the eligibility criteria will be randomized to receive LY3462817 700 mg, LY3462817 300 mg, or placebo in an allocation ratio of 2:1:1. The double-blind treatment period will establish the clinical efficacy and safety of LY3462817. The study will be evaluated for the primary objective at the end of the double-blind treatment period.

Period 2 (Visits 6 to 10; 12 weeks)

In Period 2, all subjects will receive LY3462817 to assess safety and tolerability data and explore clinical activity with additional dosing. At Week 14, participants will be evaluated for clinical benefit.

Posttreatment Safety Follow-up Period (Visits V801 and 802; 12 weeks)

Following Period 2, participants will be followed posttreatment for 12 weeks to assess safety, study drug exposure, and clinical disease activity measures.

2. Statistical Hypotheses

For the primary estimand with primary endpoint, change from baseline to week 12 in DAS28-CRP, the following 2 (confirmatory) 1-sided hypotheses are planned to be tested for LY3462817 700 mg versus placebo. Let the mean treatment difference be defined as $\mu = (\text{LY3462817 700 mg} - \text{placebo})$.

$H_0: \mu \geq 0.0$ against $H_a: \mu < 0.0$

Operationally the hypotheses will be evaluated by 2-sided tests.

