The baseline period is defined as Visit 1 through pre-dose Visit 2. The Double-blind Treatment Period starts after the first injection of study treatment at Visit 2 (Week 0) and ends on the date of Visit 6 (Week 12) or the early discontinuation visit. The Period 2 starts after the date of Visit 6 (Week 12) or the early discontinuation visit and lasts up to 24 weeks following the last injection of study treatment. Additional follow-up beyond 24 weeks may be deemed necessary and, if so, any data collected will be considered as part of Period 2.

Unless otherwise specified, baseline for the Treatment Period is defined as the last non-missing assessment on or prior to the date of the first injection of study treatment, scheduled to be given at the end of Visit 2. Any assessment collected after the first injection through the date of the Week 12 or early discontinuation visit is defined as post-baseline for the Treatment Period.

Data collected at early discontinuation visits will be mapped to the next planned visit number for that patient. For by-visit summaries, only visits in which a measure was scheduled to be collected will be summarized.

Summaries of safety data collected during Period 2 will be presented separately. Unless otherwise specified, follow-up baseline is defined as the last non-missing assessment on or prior to the date of Week 12 or the date of the early discontinuation visit.

Change from baseline will be calculated as the post-baseline value minus the baseline value. Percent change from baseline is defined as $(100 \times (\text{post-baseline} - \text{baseline}) / \text{baseline})$. If all baseline values are missing for a particular variable, the change from baseline and percent change from baseline will not be calculated.

The statistical analyses of efficacy, health outcomes, and safety measures will be performed using SAS Version 9.4 or higher. Lilly will be responsible for conducting analyses.

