4.6.1. Extent of Exposure

Duration of Exposure to Study Treatment

Duration of exposure on treatment (defined as time since first injection in days) during the Double-blind Treatment Period will be summarized by treatment arm and provided as listing. Duration of exposure on treatment will be calculated as:

(Date of last study visit during the Double-blind Treatment Period – Date of first injection + 1).

For patients who discontinue from the treatment, the date of discontinuation prior to Period 2 will be used.

Descriptive statistics for duration of exposure and the frequency and percentage of patients falling into the following ranges will be summarized: 0, >0, ≥ 7 days, ≥ 14 days, ≥ 30 days, ≥ 60 days, ≥ 84 days. The frequency and percentage of patients with duration of exposure in the following categories will also be summarized: 0 days, <14 days, ≥ 14 to <30 days, ≥ 30 to <60 days, ≥ 60 to <84 days, ≥ 84 days.

Overall exposure for each treatment arm will also be summarized in total patient years. This will be calculated as follows:

Exposure in patient years = Sum of duration of exposure (for all patients in treatment arm) / 365.25.

The analyses in Double-blind Treatment Period will be repeated for all visits in period 2 for subjects who remain on LY3462817 300 mg or LY3462817 700 mg.

Total Dose of Study Treatment

Total dose of active study treatment per subject will be summarized by active treatment arm using descriptive statistics. The total dose (mg) will be calculated as:

Total Dose = Sum over all injections received of [dose of LY (mg) prescribed per injection]

A by-patient listing of exposure duration and total dose will be provided.

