4.6.2. Adverse Events

A treatment-emergent adverse event (TEAE) is defined as an event that first occurred or worsened in severity after baseline, with baseline defined as all pre-existing conditions recorded at Visit 1 and any AEs recorded before the first dose of study intervention (that is, during the interval between Visits 1 and 2 and recorded with the time of onset before the first dose of study intervention). The MedDRA Lowest Level Term (LLT) will be used in the treatment-emergent computation. The maximum severity for each LLT before the first injection will be used as baseline. Start date of adverse events will be compared with date of first injection and the date of Visit 10 (Week 24) to determine whether an adverse event is treatment-emergent. Should there be insufficient data for adverse event start date or severity to make this comparison; the adverse event will be considered treatment-emergent.

TEAEs will be coded according to established Medical Dictionary for Regulatory Activities (MedDRA) terms and summarized by MedDRA System Organ Class (SOC) and Preferred Term.

An overview of adverse events will summarize the percentage of patients experiencing deaths, SAEs, AEs reported as reason for discontinuation, TEAEs, and AEs possibly related to study treatment.

The frequency and percentage of patients with the following will be summarized using MedDRA Preferred Term nested within SOC.

- TEAEs
- TEAEs by maximum severity
- TEAEs related to study intervention
- TEAEs leading to study discontinuation
- SAEs including death
- SAEs by maximum severity
- SAEs related to study intervention
- Deaths
- AE of Special Interests (AESIs)

Events will be sorted alphabetically by SOC and then by decreasing total frequency within SOC. For incidence counts, each patient will be counted only once within each Preferred Term and within each SOC. Percentages will be based on the number of patients in a particular treatment arm. For events that are gender-specific, the denominator and computation of the percentage will include only patients from the given gender.

Adverse events of special interest will be identified by a standardized MedDRA query or a Lilly-defined MedDRA preferred term listing.

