4.6.2.1. Hypersensitivities

Hypersensitivities will be defined using the following terms:

- Anaphylactic reaction standardized MedDRA query (SMQ) excluding the Preferred Term Anaphylactic transfusion reaction
- Angioedema SMQ excluding the Preferred Terms Oedema neonatal and Peripheral oedema neonatal
- Severe cutaneous adverse reactions SMQ Narrow Search terms and the following Broad Search terms:
 - Drug eruption
 - Drug rash with eosinophilia and systemic symptoms
 - Lip exfoliation
 - Mucosal exfoliation
 - Penile exfoliation
 - Skin exfoliation

- Stomatitis
 - Tongue exfoliation
 - Vaginal exfoliation
- Additional Preferred Terms including:
 - Asphyxia
 - Dermatitis
 - Dermatitis allergic
 - Dermatitis atopic
 - Dermatitis contact
 - Diastolic hypotension
 - Eczema
 - Eosinophilic oesophagitis
 - Erythema nodosum
 - Hypotension
 - Immediate post-injection reaction
 - Injection related reaction
 - Orthostatic hypotension
 - Photosensitivity allergic reactions
 - Photosensitivity reaction
 - Presyncope
 - Rash vesicular
 - Reaction to drug excipients
 - Red man syndrome
 - Serum sickness
 - Serum sickness-like reaction
 - Syncope
 - Type II hypersensitivity
 - Type III immune-complex-mediated reaction
 - Type IV hypersensitivity reaction
 - Toxic skin eruption
 - Urticaria contact
 - Urticaria vesiculosa

The frequency and percentage of patients experiencing treatment-emergent hypersensitivities will be summarized by treatment arm, maximum severity, SOC, and Preferred Term during Treatment Period. The frequency and percentage of patients experiencing treatment-emergent hypersensitivities will also be summarized by treatment arm and timing category (immediate, acute reaction, delayed reaction or reaction after more than 15 days).

Exposure-adjusted incidence rates (per 100 patient years) of treatment-emergent hypersensitivities within the following time intervals will be calculated as detailed below.

- ≥ 0 to ≤ 6 weeks since the date of first injection:

Interval start date = Date of first injection,

Interval end date = Date of first injection + 42 days.

- > 6 to ≤ 12 weeks since the date of first injection:
Interval start date = Date of first injection + 43 days,
Interval end date = Date of first injection+ 84 days.
- ≥ 24 weeks since the date of first injection:
Interval start date = Date of first injection + 85,
No Interval end date, Treatment Period planned for 24 weeks

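### The last exposure-adjusted interval in SAP 4.6.2.1 has no end date although event counting stops at Visit 10, so its rate may be unbiased or up to about half too low

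*SAP*

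**What the plan says.** **Interval.** SAP 4.6.2.1 splits the hypersensitivity rates into three intervals. The third is labelled "≥ 24 weeks since the date of first injection", but its start rule is "Interval start date = Date of first injection + 85", which is just after Week 12. For its end the SAP says only "No Interval end date, Treatment Period planned for 24 weeks".

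**Events.** The numerator is treatment-emergent events. Under SAP 4.6.2, "Start date of adverse events will be compared with date of first injection and the date of Visit 10 (Week 24) to determine whether" an event qualifies. Protocol 9.4.7 summarizes follow-up emergent events separately.

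**Time.** SAP 4.1 defines the Treatment Period as Period 1 plus Period 2. It says that Period 2 starts after Visit 6 "and lasts up to 24 weeks following the last injection of study treatment". SAP 1.2 instead ends Period 2 at Visit 10 and treats what follows as a separate stage: "Following Period 2, participants will be followed posttreatment for 12 weeks to assess safety".

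**Patient-years.** The only formula is in SAP 4.6.1, for overall exposure during double-blind treatment. On Period 2 it says: "The analyses in Double-blind Treatment Period will be repeated for all visits in period 2 for subjects who remain on LY3462817 300 mg" or 700 mg.

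**Other rates.** SAP 4.6.2.4 (malignancies) and 4.6.2.5 (depression) also plan rates by time interval, and plot them. For the definition they cite Section 6.14.2.1, which the SAP does not contain.

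**The concern.** A rate needs events and time at risk counted over the same window. Here the event window has a stated close and the time window does not, and one of the SAP's own period definitions carries the time window well past that close. Time after Visit 10 could then enter the denominator although no event in it can enter the numerator.

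These are the SAP's only exposure-adjusted safety rates, and hypersensitivity and malignancy are adverse events of special interest in protocol 8.3.6. With the longer denominator, a constant hazard would seem to drop after Week 12, which could be read as a risk that wanes with continued treatment. Arms hold about 20 or 40 participants, so a single event sets the rate, and two programmers working from this text could report rates that differ by a factor of two.

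**Working it through.** The documents state no exposure-adjusted rate and no person-time total, so there is no figure to reproduce. The check is day arithmetic.

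**Inputs**
- Start of last interval: Day 85 (SAP 4.6.2.1).
- Last day on which an event can count: Visit 10, Day 168 ± 7 (SAP 4.6.2; Schedule of Activities).
- Last scheduled visit: Visit 802, Day 252 ± 7 (Week 36), or 12 weeks after an early termination visit (Schedule of Activities).
- Reach of Period 2 under SAP 4.1: a last injection at Week 12 gives 12 + 24 = Week 36. A last injection at Week 24 gives Week 48, beyond the last visit.

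**Formula.** Factor = countable days ÷ denominator days = (Visit 10 day − 85 + 1) ÷ (last day of person-time − 85 + 1). A factor of 1 means no bias.

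**Everyone followed to Week 36**
- Nominal days: (168 − 85 + 1) ÷ (252 − 85 + 1) = 84 ÷ 168 = 0.50.
- Early Visit 10, late Visit 802: (161 − 84) ÷ (259 − 84) = 77 ÷ 175 = 0.44.
- Late Visit 10, early Visit 802: (175 − 84) ÷ (245 − 84) = 91 ÷ 161 = 0.57.

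**Only a share f followed to Week 36, the rest to Week 24.** The documents do not give f, so these shares are assumptions. Factor = 84 ÷ (84 + 84f).

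| f | Factor | Understatement |
|---|---|---|
| 1.00 | 0.50 | 50% |
| 0.75 | 0.57 | 43% |
| 0.50 | 0.67 | 33% |
| 0.25 | 0.80 | 20% |
| 0 | 1.00 | none |

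**Person-time closed at Week 24.** 84 ÷ 84 = 1.00, so there is no dilution.

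**What one event would show (assumed, for illustration)**
- 20 participants: 20 × 84 ÷ 365.25 = 4.60 patient-years, or 21.7 per 100. To Week 36: 20 × 168 ÷ 365.25 = 9.20 patient-years, or 10.9 per 100.
- 40 participants: 9.20 patient-years, or 10.9 per 100. To Week 36: 18.40 patient-years, or 5.4 per 100.

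**If the label governed instead of the start rule.** The interval would begin at Day 168. Only 1 of the 85 days from Day 168 to Day 252 would be countable, and the rate would be close to zero. Weeks 12 to 24 would belong to no interval.

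**The case against.** The strongest reply is that the SAP does not write the longer denominator. No sentence defines person-time for these rates, and the end-date line itself mentions a 24-week Treatment Period, which can be read as closing the interval there. Other text agrees. SAP 1.2 ends Period 2 at Visit 10. SAP 4.6.2.3 censors first infections at completion of, or early discontinuation from, the Treatment Period, gives Kaplan-Meier estimates no later than 24 weeks, and names a separate follow-up period. SAP 4.6.2.6 bounds treatment-emergent C-SSRS findings at Visit 10 or early discontinuation. This stands: a reader might infer that the rate is halved as written, and the documents do not support that as a fact. It does not remove the conflict, because SAP 4.1 defines a longer period and the interval line says outright that there is no end date.

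Follow-up to Week 36 for everyone is also an assumption. Protocol 4.1 gives participants who discontinue under Section 7 a last visit 12 weeks after the last administration, so a last dose at Week 12 leads to Week 24. The documents do not clearly say which schedule applies to those moved to standard of care at Week 14. This stands too, and it is why the result is a range.

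A reader might go further and apply the SAP 4.6.1 patient-years, concluding that the comparison flatters LY3462817. On the protocol's design, placebo has no Period 2 exposure under that rule. If 30% of LY3462817 participants continue (assumed; range 20% to 50%), whole-period rates are inflated 168 ÷ 84 = 2.0-fold on placebo and 168 ÷ (84 + 0.3 × 84) = 1.54-fold on LY3462817. The rate ratio is then multiplied by 0.77 (0.83 to 0.67). But SAP 4.6.2.1 never invokes that formula, and the planned rates are by interval, not whole-period. The arithmetic shows only why the formula should not fill the gap.

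Lastly, no test is planned on these rates, and crude frequencies and by-patient listings are also given. One event in 4.6 patient-years has an exact 95% interval of about 0.6 to 121 per 100 patient-years. That limits the importance of the point, but not the need to state the denominator.

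**Conclusion.** The SAP contradicts itself on when the last interval ends, and event counting is not aligned with every denominator that its definitions allow. The last-interval rate is understated by about half if person-time runs to Week 36 for all participants (factor 0.50 on nominal days, 0.44 to 0.57 across visit windows). The understatement is smaller if some participants have no time after Week 24, and nil if person-time closes there. Which of these applies cannot be settled from the documents.

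The interval scheme is written for hypersensitivity only. That it also governs malignancy and depression is a likely inference, since the section they cite does not exist. The label and start rule of the third interval contradict each other whichever reading is taken.

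Because the rates are descriptive and the trial has about 80 participants, this is a small but real correction.

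**What to change.** - **SAP 4.6.2.1:** end the third interval at the date of Visit 10, or at withdrawal if earlier. Apply that end to both events and person-time, for all participants in every arm.
- **Label:** reword the third interval's heading to match its Day 85 start.
- **Follow-up:** if time after Visit 10 is wanted, give it a separate interval with the events that start in it.
- **Denominator:** say that the SAP 4.6.1 patient-years are not used for these rates, because in Period 2 they cover only participants who remain on LY3462817, while events to Visit 10 count in every arm.
- **SAP 4.6.2.4 and 4.6.2.5:** replace the reference to Section 6.14.2.1 with 4.6.2.1.
- **SAP 4.1:** reconcile the length of Period 2 with SAP 1.2.

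The cost is SAP wording and one programming rule. No new data are needed.

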4.6.2.2. Infusion Site Reactions

Infusion site reactions will be defined using terms from the infusion site reactions high level term.

The frequency and percentage of patients with a treatment-emergent infusion site reaction will be summarized by treatment arm, maximum severity, SOC, and Preferred Term during Treatment Period.

The frequency and percentage of patients with infusion site reactions will be summarized by treatment arm and redness category (normal, noticeable but very mild redness, clearly red, bright red, and dark with some scar formation) during Treatment Period and during Treatment Period. Similarly, the frequency and percentage of patients with infusion site reactions will be summarized by treatment arm and swelling category (no bump, barely noticeable, clear bump but very thin, clear bump 1mm thick, clear bump 2mm thick or more) during Treatment. Finally, the frequency and percentage of patients with infusion site reactions will be summarized by treatment arm and pain category (none, mild, moderate and severe) during Treatment Period.

The duration of each treatment-emergent infusion site reaction during the Treatment will be defined and summarized in the same way as described for infectious AEs in Section 16.4.2.1.

A by-patient listing of treatment-emergent infusion site reactions will be provided.

4.6.2.3. Infections

Infectious events include infections, serious infections, opportunistic infections, infections that require therapeutic intervention, and any events involving reactivation of TB or hepatitis. Such events will be selected using the 'Infections and Infestations' SOC.

In addition to incidence of infectious AEs by MedDRA Preferred Term as described above, the frequency and percentage of patients experiencing the following types of infectious AEs (yes or no) during the Treatment Period and during Treatment Period will be provided by treatment arm.

- Gram-positive bacterial infection
- Gram-negative bacterial infection

- Mixed aerobic-anaerobic bacterial infection
- Fungal infections
- Viral infections
- Other infections
- Opportunistic infections as assessed by the investigator

The frequency and percentage of patients experiencing infectious AEs during the Treatment Period who are treated with antibiotics will be presented by treatment arm. Note that the event ID of all infectious AEs will be cross-referenced with the Concomitant Medications eCRF page, which records whether a medication was taken as a result of a specific AE. Any antibiotics will be highlighted during a medical review of the concomitant medications prescribed.

The frequency and percentage of patients experiencing infectious AEs will be presented by treatment arm and infection diagnosis during the Treatment. The frequency and percentage of patients experiencing infectious AEs will also be presented by treatment arm and primary site of infection during the Treatment Period.

The time to onset of first treatment-emergent infectious AE during the Treatment Period will be defined as follows:

Time to onset of first treatment-emergent infectious AE (in weeks) = (Start date of first infectious AE – Date of randomization +1) / 7.

Note that if an infectious AE was pre-existing prior to the date of first injection and subsequently became treatment-emergent due to worsening post-baseline, the date of worsening will be used in place of the AE start date.

If a patient does not have a treatment-emergent infectious AE during the Treatment Period, they will be censored at the date of completion or early discontinuation from the Treatment Period. Kaplan-Meier estimates of the proportion of patients not yet experiencing their first treatment-emergent infectious AE at 1, 6, 12 and 24 weeks will be provided for each treatment arm. A Kaplan-Meier plot of the time to onset will be presented by treatment arm.

The duration of each treatment-emergent infectious AE during the Treatment Period will be defined as follows:

Duration of treatment-emergent infectious AE (in weeks) = (End date of AE – Start date of AE + 1) / 7.

If an AE has not ended by the date of completion or early discontinuation from the study, including the Post-Treatment Follow-up Period, it will be censored as of that date. Descriptive statistics for the duration of treatment-emergent infectious AEs will be summarized by treatment arm. If a patient has more than one treatment-emergent infectious AE during the Treatment Period, then each AE will contribute to the analysis. If a patient does not have a treatment-emergent infectious AE during the Treatment Period, they will not be included in the analysis.

By-patient listings of patients experiencing a treatment-emergent infectious AE, infection-related deaths, and treatment-emergent opportunistic infections will be provided. The listing will include the following: patient demographics (including geographic region), concomitant medication,

results for total leukocytes, lymphocytes and total B lymphocytes, event start and stop dates, study treatment start and end dates, and the event outcome.

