7.1.1.1. Infection-related Criteria for Temporary Withholding of Study Intervention

Study intervention will be temporarily withheld if any of the following infection-related criteria occur during the study:

1. Serious or opportunistic infections, as defined in Exclusion Criteria (Section 5.2). Study intervention can be withheld until resolution of all acute clinical signs and symptoms, and completion of all appropriate anti-infective treatment (exception for LTBI, noted below). The investigator should consult with the Medical Monitor and then determine when it is appropriate to recommence study treatment.
2. If a participant is diagnosed with LTBI during the study and is treated for LTBI as follows:
 - a) Study intervention is temporarily held for at least the first 4 weeks of LTBI treatment.
 - b) If there is no evidence of hepatotoxicity (ALT/AST must remain ≤ 2 times ULN) or other treatment intolerance after receiving at least 4 weeks of appropriate LTBI therapy (as per WHO and/or CDC guidelines), then study intervention may be resumed.
 - c) The participant must complete appropriate LTBI therapy during the course of the study to remain eligible to continue to receive study intervention.
3. HBV DNA results reported as positive, or as detecting HBV DNA, but HBV DNA is below the level of quantification. The Medical Monitor should be contacted regarding study status

of the participant. Hepatitis B virus DNA testing should be repeated as soon as possible. If HBV DNA is confirmed positive, then study intervention should be discontinued.

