8.3.6. Adverse Events of Special Interest

Adverse events of special interest for this study include:

- hypersensitivity
- infusion site reactions
- infections, and
- malignancy.

Hypersensitivity

Many drugs, but particularly biologic agents, carry the risk of systemic hypersensitivity reactions. If such a reaction occurs, additional data describing each symptom should be provided to the sponsor in the eCRF.

Sites should have appropriately trained medical staff and appropriate medical equipment available when study participants are receiving study drug. It is recommended that participants who experience a systemic hypersensitivity reaction be treated per national and international guidelines.

In the case of generalized urticaria or anaphylaxis, additional blood and urine samples should be collected as described in Section 10.6, Appendix 6, Recommended Laboratory Testing for Hypersensitivity Events. Laboratory results are provided to the sponsor via the central laboratory.

Infusion Site Reactions

Symptoms of a local infusion site reaction may include erythema, induration, pain, pruritus, and edema. If an infusion site event is reported, the AE will be recorded, and additional data will be provided to the sponsor in the eCRF.

Infections

Participants will be monitored for symptoms and signs of infection after administration of LY3462817. More detailed information may be found in the IB.

Opportunistic Infections

The sponsor will identify infections considered to be opportunistic based on the publication “Opportunistic infections and biologic therapies in immune-mediated inflammatory diseases: consensus recommendations for infection reporting during clinical trials and postmarketing surveillance” (Winthrop et al. 2015).

Malignancy

Participants will be monitored for symptoms and signs of malignancy after administration of LY3462817. More detailed information may be found in the IB.

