4.9. Changes to Protocol-Planned Analyses

There is no change to protocol-planned analyses.

5. Sample Size Determination

Approximately 80 participants will be randomly assigned to study intervention. At the completion of the study, approximately 40 participants will have been randomized to LY3462817 700 mg and 20 participants will have been randomized to LY3462817 300 mg and placebo during the double-blind treatment. All randomized participants in FAS will be considered evaluable.

Assuming -1.80 and -0.75 as the DAS28-CRP change from baseline for LY3462817 700 mg and placebo, respectively, with standard deviation equal to 1.25, a 2-sided t-test with alpha = 0.05 has greater than 80% power to detect a statistically-significant difference in DAS28-CRP change from baseline at Week 12.

6. Supporting Documentation

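### The SAP's opportunistic-infection row uses the investigator's label with no definition, while the protocol has the sponsor identify these infections against a named publication; the difference is not declared

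*SAP*

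**What the plan says.** Protocol 8.3.6 introduces its list with "Adverse events of special interest for this study include" and names infections as one of four entries. Under infections, a sub-heading on opportunistic infections states: "The sponsor will identify infections considered to be opportunistic based on the publication", and gives the title of one consensus publication. Exclusion criterion 23 (protocol 5.2) cites the same publication to define opportunistic, and the infection-related withholding rule (7.1.1.1) points back to that criterion.

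SAP 4.6.2.3 first selects infectious events as a whole: "Such events will be selected using the 'Infections and Infestations' SOC". In addition to incidence by Preferred Term, it then asks for counts and percentages by arm in seven categories. The last is "Opportunistic infections as assessed by the investigator". No publication or term list is attached.

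The same section ends with listings: "By-patient listings of patients experiencing a treatment-emergent infectious AE, infection-related deaths, and treatment-emergent opportunistic infections will be provided". No assessor or definition is given there either.

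The general rule in SAP 4.6.2 reads: "Adverse events of special interest will be identified by a standardized MedDRA query or a Lilly-defined MedDRA preferred term listing". It repeats protocol 9.4.7, and no list for opportunistic infections follows. SAP 4.9 states: "There is no change to protocol-planned analyses".

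**The concern.** The protocol fixes who classifies an on-study infection as opportunistic and against what. The SAP row changes the first and omits the second. An infection that meets the publication's definition but is not labelled opportunistic at the site drops out of the row. One that the site labels opportunistic outside that definition enters it. The clinical study report could then carry a count that does not follow the definition used elsewhere in the trial. Because the listing names no assessor, the table and the listing could also disagree.

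This deserves care because LY3462817 is meant to stimulate an immune-inhibitory pathway and infections are a named event of special interest. Such events are likely to be few, so a single label is visible in the percentages.

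**Working it through.** The plan states no figure on this point, so there is none to reproduce. The check is a comparison of texts, followed by simple arithmetic for scale.

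**Step 1: the two rules side by side**

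| | Protocol 8.3.6 | SAP 4.6.2.3, tabulated row |
|---|---|---|
| Who decides | Sponsor | Investigator |
| Criterion | Named consensus publication | None cited |

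Both apply to infections arising on study, so the difference is not one of scope.

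**Step 2: does other SAP text resolve it?**

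- The special-interest rule in SAP 4.6.2 permits a standard query or a sponsor term list, which would fit the protocol. No such list is given for opportunistic infections, and the row itself names the investigator.
- Selection by the infections System Organ Class does not separate opportunistic from other infections.
- The listing of opportunistic infections is silent on assessor and definition. It neither contradicts the protocol nor settles the matter.
- SAP 4.9 and the SAP introduction both report no changes. Protocol 9.4.1 says that changes to analysis methods, with their justification, go in the SAP and the study report.

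Nothing resolves it.

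**Step 3: how far one case moves the row**

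Inputs: planned arms of 40 (700 mg), 20 (300 mg) and 20 (placebo), from protocol 9.2. SAP 4.6 adds an all-LY3462817 column, 40 + 20 = 60. SAP 4.6.2 bases percentages on the number of patients in the arm. I assume that all randomized participants are dosed. The change per reclassified participant is 100/n:

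- 700 mg: 100/40 = 2.5 points
- 300 mg or placebo: 100/20 = 5.0 points
- All LY3462817: 100/60 = 1.7 points

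**Step 4: could one label decide an arm comparison?**

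The documents give no expected count, so I assume 0 to 2 cases in the two groups compared. SAP 4.1 makes Fisher's exact test the default for categorical comparisons. With two cases in total, the splits giving the smallest two-sided p are:

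- 700 mg 0/40 vs placebo 2/20: C(20,2)/C(60,2) = 190/1770 = 0.107
- 300 mg 0/20 vs placebo 2/20: 2 × 190/780 = 0.49
- All LY3462817 0/60 vs placebo 2/20: C(20,2)/C(80,2) = 190/3160 = 0.060

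None reaches 0.05. The last is below the 0.10 level that SAP 4.1 also names, but it describes an excess on placebo. For an excess on drug, 2/40 vs 0/20 gives (780 + 190)/1770 = 0.55.

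**The case against.** The strongest reply is that this is a wording mismatch in one of seven extra breakdown rows, and much of that stands.

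- **No event is lost.** Every infection in the System Organ Class appears by Preferred Term and in a by-patient listing with concomitant medication, cell counts, dates and outcome. In a study of about 80 people, a reader could reclassify a case from these. This limits the harm but does not make the row correct.
- **Sites have the definition.** A reader might infer that there is no common criterion at all. The documents do not support that: exclusion 23 and the withholding rule put the same publication in investigators' hands. What is missing is any text linking that definition to the SAP row.
- **It is not an endpoint.** The listed special-interest event is infections, opportunistic infection is a sub-heading, and protocol 9.4.7 treats safety data descriptively.
- **The protocol plans no such table.** Protocol 9.4.7 does not call for an opportunistic-infection tabulation, so SAP 4.9 can be read as literally true of planned analyses. Even so, once the SAP adds the row, it uses a different classification from the one in protocol 8.3.6 and does not say so.
- **Version gap.** The SAP rests on the protocol dated 05AUG2020. The protocol supplied cites data to 02 September 2020, so it is later. The visible part of the amendment log does not list 8.3.6, and the rest is not available. Lag might explain the mismatch, but the texts would still need to be reconciled.

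**Conclusion.** The point holds as a real, undeclared conflict over assessor and criterion, limited to one descriptive row and possibly its listing. Following the SAP can give a different count from the one that the protocol's definition would give. Each reclassified participant is worth 2.5, 5 or 1.7 percentage points, depending on the column, if the planned arm sizes are met and all randomized participants are dosed. The primary endpoint and every planned efficacy test are untouched.

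A reader might go further and infer that one misclassified case could create or erase a safety signal, or that many sites would apply divergent labels. The documents support neither. With an assumed 0 to 2 cases, no comparison reaches 0.05, and cases this rare would be read individually from the listings. Neither document states a number of sites. The correction is worth making because it is cheap and the protocol has already settled who does the classification, not because a trial conclusion depends on it.

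**What to change.** In SAP 4.6.2.3, base both the tabulated row and the listing of treatment-emergent opportunistic infections on the sponsor's identification against the publication cited in protocol 8.3.6. Show the investigator's assessment alongside, labelled as such. The term list or review rule should preferably be fixed before any unblinding and applied without knowledge of treatment. Protocol 8.3.6 does not itself require this, but it fits the rule in protocol 9.5 that the SAP be final before unblinding.

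If the sponsor prefers to keep the investigator's assessment as the tabulated category, declare and justify the departure in SAP 4.9.

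The cost is a change of SAP wording and a read of the infection terms in about 80 participants. Protocol 8.3.6 already gives the identification to the sponsor; the blinding and timing are the only additions. No data collection, dosing or stopping rule changes.
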